### **5.4 Sample size justification for secondary distribution cohorts (quantitative data collection)**

The primary aim of secondary distribution is to increase uptake of HIV testing services among the intended users. Through the secondary distribution cohorts, we will investigate factors associated with use of an HIVST as reported by the index individual. To meet this aim, our sample size is based on two key factors considered *a priori* to influence reported use of the HIVST: knowledge of partners HIV status in the ANC cohort and HIV status disclosure in the cohort of individuals who know their HIV-positive status. There limited evidence of factors associated with use of a secondary distribution HIVST. However, in both groups, we anticipate that reported use of the HIVST will be approximately two-times higher among pregnant

women who state they know their partners HIV status and among HIV-positive individuals who have disclosed their HIV status to their partner.

In a cohort study among women attending ANC in Kenya, ~87% reported distributing the HIVST to their primary partner and that the partner used the HIVST [14]. This was in a clinical trial scenario and so using this figure and extrapolating to a more real life scenario, we hypothesise that in this study among individuals who accept an HIVST, ~60% of women in ANC who report knowing their partners HIV status and ~60% of individuals who report having disclosed their HIV-positive status to their partner will report that their partner used the HIVST at 1-month follow-up. To be conservative in our estimates, we have assumed that 40% of those not reporting these factors will report that their partner used the HIVST. Based on these estimates we require a sample size of approximately 300 per cohort (~600 total) to have at least 80% power to detect this association at the p=0.05-level.

We anticipate that up to 30% of individuals who accept the offer may be lost to follow-up. To account for this potential loss to follow-up, we will therefore recruit approximately 450 individuals per cohort (approximately 900 individuals total) to maintain at least 80% power to detect this association at the p=0.05-level.

As the cohort will be recruited through the exit interview, we will continue with the exit interviews until we have reached the required sample size of approximately 450 individuals per cohort (~900 individuals overall across the two cohorts) reporting that they have accepted an offer of a secondary distribution HIVST and consenting to the follow-up within 1-month.

We plan to follow-up the intended user of the HIVST to measure linkage to confirmatory testing, care and prevention services. However, these results will be descriptive to understand pathways into care. The study is not powered to explore factors associated with linkage.

## **6. Data Collection and Management**

---

Zambart has extensive experience ensuring quality data management. This include a Quality Management Plan (QMP) and Standard Operating Procedures (SOP) developed for each study based on study design, data collection instruments and data analysis procedures, with routine data quality audits conducted for quality assurance purposes.

### **6.1 Qualitative Data**

Qualitative data will be collected through handwritten field notes of different observations (observations of the interactions between individuals and SFH staff distributing HIVST, observations of individuals navigating the health facility system or the settings for the other models, observations of interactions between individuals who accept offer of HIVST for secondary distribution and their partners), handwritten notes of mapping activities, and interviews (IDIs, FGDs). Field notes will be written in notebooks designated for each model and securely kept in the social science lockers. The field notes will then be typed and stored on a password protected computer. Transcripts of IDIs and FGDs will also be kept on a password protected computer.

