#### **Observations, in-depth interviews and focus-group discussions**

Observations will be conducted to observe the process of HIVST distribution and the interactions between staff distributing HIVST, the people and the general setting.

Observation checklists will be developed and utilized by qualitative research assistants to collect and document contextual activities happening at the distribution points, in the community and in qualitative cohort participants' homes/environments when interviews are conducted in these places, or if they visit the homes for any reason. IDIs will be conducted with purposefully selected participants to obtain their perspective on issues pertaining to HIVST distribution and to explore factors that influence access, acceptance, utilisation and linkage to confirmatory and prevention and care services. Focus groups discussions will be conducted with purposefully selected community members to obtain community perspectives on HIVST distribution including secondary distribution.

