## 5. Recruitment of study participants

---

All adults and adolescents aged 16 years or older (age of consent for HIV testing in Zambia) accessing HTS in clinics where HIVST distribution is being implemented are eligible for participation.

Specifically, individuals will be eligible to participate in data collection for the case studies if they:

- Are aged 16 years or older, and
- Able and willing to provide informed consent.

An individual is not eligible for participation in the study if they are:

- Under 16 years of age
- Unable and unwilling to provide informed consent
- Individuals not offered an HIVST kit, or
- If there is anything that, in the opinion of the investigator, would preclude informed consent or make study participation unsafe.

For the secondary distribution cohorts, participants are eligible if they meet these criteria and they are attending ANC or HIV testing and treatment services where secondary distribution of test kits is being offered. Informed consent will be sought for an exit interview and individuals who report accepting an offer of HIVST for secondary distribution to a partner will be eligible for a follow-up interview. Partners (intended users) of index individuals who collect an HIVST for secondary distribution will also be eligible for follow-up, providing consent is gained from the index individual at their follow-up interview and from the intended user.

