Twelve individuals (6 from the ANC and 6 from HIV+ individuals) recruited in the secondary distribution cohort will be purposively selected to participate in the qualitative cohort to explore the contextual factors affecting secondary distribution HIVST in ANC and through HIV-positive individuals. Individuals selected to participate in the cohort must have self-tested, and accepted secondary distribution on behalf of their partner. Using purposeful sampling, age, and gender will be taken into account to ensure a fair distribution of participants. Qualitative research assistants will spend extended times in the homes of the participants, using the rapport created to generate detailed data on participants' experiences with HIVST and particular the secondary distribution models. Such an ethnographic approach does not necessarily require many participants. RAs will inform quantitative cohort participants that they may be approached by researchers conducting qualitative research and asked to enrol in a qualitative cohort and that they will be asked to consent for this activity. Qualitative RAs will then approach the 12 individuals selected for the qualitative cohort and schedule interviews with them within 5 days. Follow-up interviews will be conducted immediately after the follow up visit for the quantitative cohort interviews. A key aspect of the qualitative cohort will be the extended contact with participants by the researchers in the participants' preferred milieu while at the same time conducting participatory research activities. The rapport created will be critical for prompting participants to share their experiences.

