## **8.2 HIVST procedures**

We are not requesting informed consent for individuals accepting HIVST kits because distribution of HIVST kits is now standard practice in Zambia. Multiple partners are providing test kits in the country including PEPFAR, MOH from Global Fund as well as the STAR

consortium. The national Virus Reference Laboratory is monitoring the quality of the test kits. Distribution will be conducted by MOH staff and staff of implementing partners who will be trained to adhere to national and international best practice for HTS, stressing that HIV testing is a voluntary process. HIVST distributors will be trained on provision of pre-test information, including how to perform the self-test, interpret results, and link to confirmatory testing, ART or VMMC services. Observations in communities and in health facilities will be explained to individuals who are being observed and they will have the opportunity to refuse observation. Written consent will not be requested as this would likely alter behaviour. Observation notes will never identify individuals.

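### Home observation of couples in the qualitative cohort has no stated step for the partner's agreement, although some index patients are expected not to have disclosed their HIV status

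*Protocol*

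**What the plan says.** **What is observed.** Section 6.1 lists among its handwritten field notes "observations of interactions between individuals who accept offer of HIVST for secondary distribution and their partners".

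**Where.** Section 5.2 says of the qualitative cohort: "Qualitative research assistants will spend extended times in the homes of the participants". Section 4.2 has observation checklists used "in qualitative cohort participants' homes/environments when interviews are conducted in these places, or if they visit the homes for any reason".

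**When.** Under 5.2 the qualitative assistants approach the selected individuals and "schedule interviews with them within 5 days". Section 4.2 puts the first of two interviews at recruitment. For the second, 5.2 says: "Follow-up interviews will be conducted immediately after the follow up visit for the quantitative cohort interviews". Consent to join the qualitative cohort is sought from the index participant; that paragraph does not mention the partner.

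**Partner safeguards.** Section 5 makes partners eligible for follow-up "providing consent is gained from the index individual at their follow-up interview and from the intended user". Section 5.2 adds that the index patient is asked for this permission only if he or she reports that the partner used the kit, and that the partner gives written consent before being interviewed.

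**Consent for observation.** Section 8.1 exempts observations from written consent. Table 3 has a row for participant observations (verbal consent) and a separate row for observations (none). Section 8.2 promises that observation in communities and health facilities will be explained and may be refused, and that notes will not identify anyone. It then says: "Written consent will not be requested as this would likely alter behaviour".

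**The concern.** The partner is protected by a careful sequence when he or she is to be surveyed, but by no stated sequence when he or she is to be watched at home with the index patient. The second activity is at least as intrusive, and it can come first.

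What is at stake is disclosure. Section 5.4 sizes the HIV-positive cohort on a comparison of index patients who have and have not disclosed to their partner, so undisclosed status is part of the design. A researcher from an HIV study who spends long periods in the home may reveal that status or start a conflict. Seeking the partner's verbal agreement on the spot does not remove the risk: it tells the partner about the study before the index patient has agreed to the approach.

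The protocol recognises inadvertent disclosure as a harm in 8.1, but only in relation to parental consent. Section 10.2 accepts that giving a woman a kit for her partner may carry serious risks, including violence. Section 5.1 excludes the two secondary distribution models from the community-based social-harm mechanisms and relies instead on interviewing and observing qualitative participants, though 8.4 and 10.2 also describe a general reporting system.

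**Working it through.** The point concerns the order of steps and the consent rule, so no formula applies. The check sets the sections side by side.

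1. *Is observing the couple planned?* Yes. Section 6.1 names it as a data source but gives no start time.

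2. *Can it happen at home?* Yes. Section 5.2 plans prolonged stays, and 4.2 has checklists completed in "homes/environments when interviews are conducted in these places, or if they visit the homes for any reason".

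3. *Can home contact precede the partner steps?* Yes, though the protocol does not say that it must. The first index interview is at recruitment (4.2) or is scheduled within 5 days (5.2). The partner steps come at about 1 month. Taking a month as 30 days, 30 − 5 = 25 days, so home contact can come between 3 and 4 weeks earlier.

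4. *Do the partner steps ever reach every observed partner?* No. Section 5.2 applies them only where the index patient reports kit use. A partner who did not use the kit is never approached under that procedure, yet falls within what 6.1 allows to be observed.

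5. *Which consent rule covers observation at home?* This cannot be determined. Table 3 offers verbal consent or none. Section 8.2 names neither homes nor partners, and no section says who asks the partner, when, or how this is done if the index patient has not disclosed.

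6. *Is there a recruitment step for partners in the qualitative cohort?* Appendix 4 contains a first-interview guide for the primary partner, but the 5.2 paragraph on that cohort describes no such step. The guide's opening script says that kits are given out at the ART clinic and ANC, which could itself suggest ART attendance.

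7. *How many people?* Section 5.2 gives 12 index patients, 6 per cohort; section 4.2 gives 24, 12 per cohort. The HIV-positive part is therefore 6 or 12. The protocol does not state the share who have not disclosed. If it were 20% to 50% (an assumption, for scale only), the number would run from 6 × 0.20 = 1.2 to 12 × 0.50 = 6, or about 1 to 6 people. The count of couples is a ceiling, because the exit questionnaire allows for partners who live elsewhere.

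**The case against.** The strongest reply is that the protocol does not contradict itself. Sections 5 and 5.2 govern recruitment of the intended user for the follow-up survey and are not written as a rule for observation. That is correct: this is a gap between sections.

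A reader might infer that partners are observed without consent from within days of recruitment. The documents do not support that. The 5-day limit covers scheduling the index patient's interview. The index first-interview guide asks how the kit was offered at home, so it presupposes that the kit has been delivered. Prolonged stays in the home fit the verbal-consent row of Table 3 better than the other row. Homes in the study communities could be read as covered by 8.2. The template consent forms (Appendix 2) were not in the text at hand, so a clause on partner observation cannot be ruled out.

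Existing safeguards also count. Index patients consent separately to the qualitative cohort, and 8.1 and 8.4 let participants choose a safe and private interview place. This lowers the risk for an index patient who avoids meeting at home, but it gives the partner no say.

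A reader might also infer bias in the 1-month primary outcome, on the ground that visits prompt kit use. Nothing in the documents shows this, and the scope is negligible. With 450 × 0.70 = 315 followed per cohort, 12 visited participants and 50% use without visits, the extreme case in which every visited non-user changes is 12 × 0.50 / 315 = 1.9 percentage points.

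What stands is that the applicable consent rule is unspecified and that no visible section ties the partner's agreement to observation of the couple.

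**Conclusion.** The point holds as a gap in participant protection. The protocol plans home observation of couples, allows home contact before any partner step, and does not say which consent rule applies or how the partner's agreement is obtained. Few people are affected: at most 12 or 24 couples, 6 or 12 of them with an index patient from the HIV-positive cohort. A disclosure to a partner cannot be reversed, however, and the remedy is cheap, so the change should be made.

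The conclusion rests on the visible text. If a consent form already covers partner observation, sections 4.2, 5.2, 6.1 and 8.2 and Table 3 still need to agree with it. The finding does not establish that partners will be observed without consent, and it does not bear on the primary analysis.

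Nor does it justify allowing home visits only where status has been disclosed. Index patients who have not disclosed are one of the two groups that 5.4 compares and matter for the objective on social harms, so such a rule would remove them from the home-based work.

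**What to change.** Reconcile sections 4.2, 5.2, 6.1 and 8.2 and Table 3 as follows.

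- In 5.2 and 6.1, state that interactions between index patient and partner are observed or recorded only after the index patient has agreed that this partner may be approached and the partner has consented. Make the same condition apply to the home checklists in 4.2.
- In Table 3, add a row for home observation of couples that requires the agreement of both people.
- In 8.2, extend the explanation and the right to refuse to homes and to partners.
- Until both agreements are in place, hold qualitative interviews in a private place that the index patient chooses. This largely restates what 8.1 and 8.4 already offer.

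The cost is wording, with no extra staff or participants. The real downside is that some couple observations will happen later or not at all. The loss may be greater among couples where status is undisclosed, because those index patients may more often decline the approach. They can still be interviewed themselves.

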## **6.2 Quantitative process data**

At each HIVST distribution point, SFH will use trained HIVST distributors to collect paper-based process data. Trained SFH distributors will capture data on socio-demographics such the age of the client, occupation and whether an individual has accepted HIVST or not (Appendix 3). For individuals who HIVST within the distribution points, the distributor will also be available to collect data related to usage and test results.

SFH will assess the quality and accuracy of process data through supervisory visits. Zambart will use the SFH collected process data in the case studies for all the models of distribution. If needed, and in consultation with SFH, additional data will be collected by adding a few questions to the SFH data collection tool.

Data will be manually double entered into a specifically designed database (Microsoft Access). This data will then be cleaned according to data SOPs. All computers are password protected and all data will be stored on a regularly backed-up secure server held at Zambart. No names or personal identifiers will be entered.

## **6.3 Quantitative secondary distribution cohort data**

Quantitative data for the exit and follow up surveys will be electronically captured using password-protected electronic devices (EDCs). Data will be synchronized to a central server at Zambart offices. Quantitative data will be checked on a daily basis for errors. If required, additional trainings will be provided to the RAs. To ensure quality data is collected, the EDC program will encrypt survey data including the names, addresses and GPS-coordinates of the visited distribution point or households to minimize the risk of identification of participants by individuals other than RAs. In addition, Zambart will assess quality through monthly supervisory monitoring visits. All data will be cleaned and analysed using Stata software (Stata Corporation, College Station, Texas, USA). Analyses will be carried out together with the London School of Hygiene and Tropical Medicine.

## **6.4 Storage of data and Record keeping**

All the source information collected will be stored for 7 years after the study has ended after which the data will be destroyed. All paper copies that will have the participants' personal information will be kept securely in a locked cabinet in a locked room that is accessed by only assigned study staff. All electronic data will be stored on a server and will be encrypted and password protected and will only be accessible by the assigned staff. Paper copies without participants' personal information will be store in a locked room accessible by assigned staff.

## **7. Statistical Analysis**

---

### **7.1 Qualitative data analysis**

In-depth interviews and FGD will be audio-recorded. Qualitative RAs will play the recordings and transcribe the recording. A draft codebook will be developed earlier, before fieldwork using the objectives of the qualitative enquiry. It will be reviewed during field work and transcription to take into account emerging issues. The initial codebook will be developed with reference to the contextual factors which the study will be exploring and later reviewed for the emerging issues from the IDIs, FGDs, and field notes. As the particular design used for this study is not grounded theory, no attempt will be done to conduct a constant comparative analysis to reach saturation. However, having extended contacts with participants and tools with scripted probes will help to generate detailed and rich experiences by the participants. Qualitative RAs will transcribe the interviews straight onto special designed matrices. These matrices will contain thematic areas found in the codebook which will have been reviewed at this stage. This will enable the interpretation and comparison of the findings within specific thematic areas as well as across themes, participants, and distribution models. In the long term, all interviews will be fully transcribed by re-listening to the recordings, imported into Nvivo or Atlas ti and coded using a revised codebook.

### **7.2 Process Data**

All paper-based data will be coded and entered using Microsoft Access. We will use descriptive analysis to describe the numbers of people who were offered a test, proportion who accepted HIVST and reasons for not accepting the offer. The data will be segregated by age and distribution model.

### **7.3 Quantitative secondary distribution cohort data**

For the quantitative data arising from the secondary distribution cohorts, we will conduct analyses separately for the ANC and HIV testing and treatment cohorts. We will use descriptive analyses to describe the proportion of individuals accepting an offer of HIVST and the proportion who report that their partner used the HIVST. We will use standard logistic regression adjusting for study site to explore factors associated with accepting an offer of HIVST and with reported use of the HIVST.

Although the index individuals will be asked about linkage to care at 1-month follow-up, we will measure linkage to care using data from the intended users followed-up within 3-months after distribution. Linkage will be measured as the number of individuals reported to have linked to care (defined as accessing confirmatory testing services or attending an HIV care clinic for HIV-positive individuals or accessing VMMC services for HIV-negative males) among those who reported use of the HIVST.

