All individuals, regardless of whether they take an HIVST kit for primary or secondary distribution, will be informed of the follow-up services available to them and their partners (if applicable) at the health facility. Individuals will be informed that the HIVST is a screening test, such that if the test is reactive they will need to attend the health facility for confirmatory testing. Confirmatory testing will be conducted using Determine HIV™ and SD Bioline™ in line with Zambian HIV testing guidelines [3]. Individuals will also be informed that a non-reactive test does not require any confirmatory testing, but that they should return to the health facility to link to prevention services, including VMMC or to obtain a supply of condoms.

For the secondary distribution models, staff training will include additional steps to ensure that index patients understand how to demonstrate the use of the HIVST to their partner, and to communicate the next steps to be followed for a reactive or non-reactive result. SFH distributors will request that index patients collecting a secondary distribution HIVST kit for their partners to inform their partner about the availability of HIV-related follow-up services, including confirmatory testing where the HIVST is reactive.

[figure not shown]

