**Figure 2: Schematic of the quantitative and qualitative cohort in ANC and ART models**

For the secondary distribution cohorts, we will measure individual- and couple-level factors associated with acceptability to the index patient and intended user including: sex, age, previous HIV testing history, newly diagnosed or previously undisclosed HIV, relationship of the distributor and intended user (including type of relationship, age differential, measures of equality and empowerment), history of gender based violence and clinic from which the Index was recruited (ANC or HIV testing and treatment services).

The primary outcome of the secondary distribution cohorts is the:

- 1) Proportion of index patients who accepted an offer of secondary distribution HIVST kit(s) who report that their sexual partner(s) used the HIVST kit,

Secondary outcomes are the:

- 1) Proportion of index patients accepting an offer of HIVST kit(s) for secondary distribution,
- 2) Proportion of index patients who accepted an offer of a secondary distribution HIVST kit(s) who report that their partner used the HIVST kit(s) and linked to prevention or care services within 1-month of distribution

- 3) Proportion of intended recipients who self-report a) having used an HIVST kit and b) having attended confirmatory HIV testing, or HIV prevention or HIV care services within 3-months of distribution.

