### **7.4 Cost data**

Cost data will be analysed separately by the economics team in STATA 14. Costs will be descriptively categorised into direct and indirect costs. To assess the economic burden HIVST,

we will compare sum of patients' direct non-medical and indirect costs with the household per capita expenditure. We will use a multivariable Tobit regression model to determine cost predictors.

Among individuals participating in the follow-up survey, we will describe reported use of the HIVST and investigate factors associated with reporting use of the secondary distribution HIVST. We will also describe linkage to ART or voluntary medical male circumcision, and time to linkage to care. Linkage data will primarily rely on reported use by the index individual, but we also aim to describe this among the intended users if consent is provided to follow-up partners and partners consent to participate in the study.

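### Sections 7.3 and 7.4 name opposite main informants for linkage, and the 7.3 formula keeps in its denominator users with no practical way to count as linked

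*Protocol*

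**What the plan says.** **Informant and window.** Section 7.3 acknowledges that index patients are asked about linkage at 1 month, and then says "we will measure linkage to care using data from the intended users followed-up within 3-months after distribution". Section 7.4, in a cohort paragraph placed under the heading on cost data, says "Linkage data will primarily rely on reported use by the index individual" and treats the partners' own reports as an additional aim, subject to consent.

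**Formula.** Section 7.3 counts a person as linked on this rule: "defined as accessing confirmatory testing services or attending an HIV care clinic for HIV-positive individuals or accessing VMMC services for HIV-negative males". The denominator is the group described by "among those who reported use of the HIVST", with no restriction by test result, sex or circumcision status.

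**Outcome list.** Section 4.3.2 has two separate secondary outcomes on linkage. Outcome 2 is the index patient's report at 1 month. Outcome 3 is the intended user's own report, and its linkage part reads "having attended confirmatory HIV testing, or HIV prevention or HIV care services within 3-months of distribution". There, any HIV prevention service counts.

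**What users are told.** Under section 3, "a non-reactive test does not require any confirmatory testing", but people with that result are advised that "they should return to the health facility to link to prevention services, including VMMC or to obtain a supply of condoms".

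**The concern.** Two stated rules conflict, so this is not detail left to an analysis plan.

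First, the choice of main informant also fixes the time window (about 1 month or 3 months), the questionnaire and the sample (index patients who were followed up, or partners who were reached and consented). An analyst who follows 7.4 reports a different quantity from one who follows 7.3. Section 4.4.2 costs linkage from the service use reported in the cohort, so the choice may also affect the economic results.

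Second, numerator and denominator in 7.3 do not match. A non-reactive user who follows the section 3 advice and collects condoms is a success under outcome 3 and a failure under 7.3. HIV-negative women and men already circumcised are counted as failures for not using a service that does not apply to them. One pooled proportion then mixes care after a reactive test with VMMC uptake and is hard to interpret.

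**Working it through.** **Step 1. Which section is the outlier?** The documents state no linkage rate, linkage sample size or linkage power, so there is no figure to reproduce. The places that bear on the source are:

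| Place | Source of linkage data |
|---|---|
| Summary and section 2.2, objective 11 | Intended user, about 3 months |
| Section 4.3.2, text and outcome 3 | Intended user, about 3 months |
| Section 4.3.2, outcome 2 | Index patient, 1 month (a separate outcome) |
| Section 5.4, last paragraph | Follow-up of the intended user |
| Section 7.3 | Intended user, within 3 months |
| Section 7.4 | Index patient as the main source |

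Only 7.4 makes the index patient the main source. It also promises time to linkage. In Appendix 3 the index follow-up questionnaire records whether the partner linked and for which service, but no linkage date. Dates of registration for care and of starting ART are in the intended-user questionnaire. Section 7.4 also speaks only of ART and VMMC, and leaves out the confirmatory testing that 7.3 and outcome 3 count.

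**Step 2. Who lacks a route under 7.3?**

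- HIV-negative women: section 10.2 foresees men at HIV testing and treatment services taking a kit for a female partner. In the ANC model, Appendix 1 gives male partners as the target, so this affects one cohort only.
- HIV-negative men already circumcised: the intended-user questionnaire has this as a response option for not seeking VMMC.

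The documents show that both groups are expected but give no share for either.

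**Step 3. Effect of the denominator.** Let L be linkage among users able to meet the definition and e the share of users who are not.

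Reported linkage = L × (1 − e)

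| Assumed L | e = 10% | e = 20% | e = 30% | e = 50% |
|---|---|---|---|---|
| 50% | 45% | 40% | 35% | 25% |
| 70% | 63% | 56% | 49% | 35% |

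The relative understatement equals e. To see what e might be, write e = (1 − pos) × [1 − (1 − fem) × (1 − circ)], where pos is the reactive share, fem the share of women among HIV-negative users and circ the share of HIV-negative men already circumcised. All values are assumptions, with pos = 10%:

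- fem = 0, circ = 20%: e = 0.90 × 0.20 = 18%, so the formula cannot exceed 82%.
- fem = 0, circ = 40%: e = 0.90 × 0.40 = 36%; ceiling 64%.
- fem = 30%, circ = 20%: e = 0.90 × (1 − 0.70 × 0.80) = 39.6%; ceiling 60.4%.
- fem = 30%, circ = 40%: e = 0.90 × (1 − 0.70 × 0.60) = 52.2%; ceiling 47.8%.

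The last two lines can apply only to the HIV testing and treatment cohort. All four take it that no non-reactive user qualifies through confirmatory testing.

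**Step 4. Selection into partner follow-up.** Under section 5.2 a partner is approached only if the index patient reports that the kit was used and gives permission; the partner must then be reached and consent. Let f be the share of users followed up. Linkage among all eligible users is f × L(followed) + (1 − f) × L(not followed), and 7.3 reports L(followed) × (1 − e).

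Assume f = 50%, with linkage of 60% if followed up and 30% if not. Linkage among all eligible users is 0.5 × 60% + 0.5 × 30% = 45%. The 7.3 formula gives:

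- e = 10%: 54%, too high
- e = 20%: 48%, too high
- e = 30%: 42%, too low

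Break-even is e = 1 − 45/60 = 25%. With no selection (50% in both groups), any e above zero gives a figure that is too low.

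**The case against.** **Objective 11 is already tied to the intended user.** This largely stands. A reader might infer that objective 11 would get two answers from the same data. It would not: the index and partner reports are different data, and the objective, outcome 3 and sections 4.3.2, 5.4 and 7.3 agree on the partner. What remains is one sentence in 7.4 that says the opposite and has to be corrected.

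**The linkage result need not be biased low.** This stands. A reader might infer a net downward bias from the denominator, but step 4 shows that selective follow-up can outweigh it.

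**Some of these users could still qualify.** This stands in part. In 7.3 it is unclear whether the restriction to HIV-positive people covers the confirmatory-testing limb, so it cannot be said that a non-reactive user can never count. In practice section 3 says such testing is not needed, and the questionnaire item on it sits in a section for people who self-tested positive. Only an open item on services used could record it.

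**No comparison between cohorts is planned.** This stands. Section 7.3 analyses the cohorts separately, so a distorted comparison between them is not a harm the plan creates.

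**Linkage is secondary.** This stands. Section 5.4 calls these results descriptive and says the study is not powered for factors associated with linkage. That limits the weight of the point, but a descriptive proportion still needs one source and a denominator that fits its numerator.

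**Conclusion.** The point holds in two parts. Sections 7.3 and 7.4 contradict each other on the main informant for linkage, and so on window and sample, with 7.4 the outlier. The 7.3 formula is narrower than outcome 3 and divides by users who have no practical way to meet it, which understates linkage among users eligible for the counted services by the relative share e.

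The size of e cannot be derived from the documents. The 18% to 52% in step 3, and the corresponding ceilings, rest wholly on assumed shares. The net direction of bias is also unknown, because it depends on how followed-up partners differ from the others. The problem with female partners is confined to the HIV testing and treatment cohort. The primary outcome (reported kit use) and the sample size are unaffected. This is a correction of wording to a secondary, descriptive outcome.

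**What to change.** 1. In 7.4, correct the linkage sentence so that intended-user reports within 3 months are the main source for objective 11. Keep the index report at 1 month as secondary outcome 2. State the selection of followed-up partners as a limitation.
2. In 7.3, align the prevention limb with outcome 3, so that any HIV prevention service counts.
3. Report linkage by self-test result:
   - reactive users: confirmatory testing or HIV care;
   - non-reactive users: any prevention service;
   - non-reactive men not already circumcised: VMMC.
4. Show users whose result is unknown or undisclosed as a separate category. The questionnaire allows both answers, and a split by result alone would drop these users without notice.

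The cost is wording in two sections. Sex, self-test result, service use and circumcision status are already in the intended-user questionnaire. The subgroups are smaller, so the intervals will be wider, which is acceptable for an analysis the protocol already calls descriptive. The fix does not remove the selection of partners; it only makes it visible.
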